| BNP | Brain natriuretic peptide |
| BP | Blood pressure |
| CBC | Complete blood count |
| CFR | Code of Federal Regulations |
| CIOMS | Council for International Organizations of Medical Sciences |
| CL | Apparent systemic clearance |
| C_{max} | Maximum observed whole blood radioactivity |
| CMR | Cardiac magnetic resonance |
| CNR | Contrast to noise ratio |
| COVID-19 | Coronavirus-19 |
| CR | Complete response |
| CRF | Case report form |
| CRO | Contract or Clinical Research Organization |
| CT | Computerized tomography |
| CTCAE | National Cancer Institute Common Terminology Criteria for Adverse Events |
| DBP | Diastolic blood pressure |
| ECG | Electrocardiogram |
| ECOG | Eastern Cooperative Oncology Group |
| EDC | Electronic data collection |
| EOS | End of study |
| ET | Early termination |
| FSH | Follicle stimulating hormone |
| GCPs | Good clinical practices |
| HIPPA | Health Insurance Portability and Accountability Act |
| HR | Heart rate |
| HRT | Hormone replacement therapy |
| IB | Investigator's Brochure |
| ICF | Informed consent form |
| ICH | International Conference on Harmonisation |
| IEC | Independent Ethics Committee |
| IND | Investigational new drug |
| iOSAT | Potassium iodide (KI) 130 mg |
| IRB | Institutional review board |
| IRR | Infusion-related reaction |

IV Intravenous

λz Terminal elimination rate constant
LAR Legally authorized representative

LDH Lactate dehydrogenase

MedDRA Medical Dictionary for Regulatory Activities

MRI Magnetic resonance imaging
NOAEL No-observed-adverse-effect level
NSAIDs Nonsteroidal anti-inflammatory drugs

NT-proBNP N-terminal prohormone of brain natriuretic peptide

NYHA New York Heart Association

OTC Over the counter

PBS Phosphate-buffered saline PET Positron emission tomography

PK Pharmacokinetics
PT Preferred term
RBC Red blood cell
ROI Region(s) of interest
SAE Serious adverse event

SAP Serum amyloid P-component; statistical analysis plan

SBP Systolic blood pressure

scFc Single chain Fc
SD Standard deviation
SNR Signal to noise ratio
SoA Schedule of Activities
SOC System organ class

SOP Standard operating procedure

SPECT Single-photon emission computerized tomography

SpO₂ Peripheral blood oxygen saturation level SUSAR Suspected unexpected serious adverse reaction

SUV Standardized uptake value

 $t_{1/2}$ Apparent terminal elimination half-life TEAE Treatment-emergent adverse event

T_{max} Time of maximum observed whole blood radioactivity

TnI Troponin I

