2.2.2 Description of ¹²⁴I-AT-01

¹²⁴I-AT-01 is an amyloid-reactive synthetic peptide (p5+14 or APi1832) radiolabeled with ¹²⁴I under development for use as a PET/CT imaging agent for the detection of amyloid in abdominothoracic organs or tissues of patients with systemic amyloid disease. AT-01 (p5+14 or APi1832) is a synthetic, all natural, 45 amino acid peptide (MW = 4763.46 Da) with a net +12 positive charge that has been shown to specifically bind to amyloid *in vitro* and *in vivo* (Wall 2015).

Clinical experience with ¹²⁴I-AT-01 is derived from Study AMY1001 (NCT: NCT03678259), a single-center, open-label, exploratory, Phase 1/2 PET/CT imaging study to detect amyloidosis in 57 subjects, 50 of which had systemic amyloidosis, two (2) of which were asymptomatic ATTR carriers, and five (5) of which were healthy volunteers. The primary outcome measure was

localization of AT-01 using PET/CT imaging following a single dose via intravenous (IV) infusion. Overall, 124 I-AT-01 was well tolerated, with no deaths or drug-related serious adverse events. The gender-averaged, whole-body, effective dose for 124 I-AT-01 in the first three subjects was estimated to be 0.24 ± 0.02 mSv/MBq (8.7 mSv/mCi). The whole blood radioactivity half-life was 21.9 hours. 124 I-AT-01 was detected in one or more organs in >90% of patients with systemic amyloidosis, including detection in the heart, kidney, liver, and spleen. 124 I-AT-01 was detected in the liver and kidney in one (1) of five (5) healthy volunteers (both organs were identified in the same subject).

A detailed description of the chemistry, mechanism of action, and nonclinical pharmacology of ¹²⁴I-AT-01 is provided in the Investigator's Brochure (IB).

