5.1 Inclusion Criteria

Subjects are eligible to be included in the study only if all the following criteria apply:

- 1) Understands the study procedures and is capable of giving signed informed consent, as described in Appendix 1, which includes compliance with the requirements and restrictions listed in the informed consent form (ICF) and in this protocol.
- 2) Male or female \geq 18 years of age.
- 3) Has a history of AL or ATTR systemic amyloidosis with at least one organ with clinically demonstrable amyloid involvement defined by:
 - a) For AL systemic amyloidosis:
 - i) Positive tissue (e.g., fat-pad, gastrointestinal tract, etc.) biopsy for AL amyloid, and
 - ii) Achieved a hematologic very good partial response (VGPR) or complete response (CR) based on their most recent assessment and within 12 months of screening, and
 - iii) At least one of the following:
 - (1) Cardiac, renal, or liver biopsy positive for amyloid, or
 - (2) NT-proBNP \geq 650 pg/mL, or
 - (3) Left ventricle septal wall thickness ≥12 mm by echocardiogram or cardiac magnetic resonance (CMR), or
 - (4) 24-hour urine protein >500 mg, or
 - (5) Urine albumin-to-creatinine ratio (UACR) >300 mg/g.
 - b) For ATTR (wild type or variant) systemic amyloidosis:
 - i) Positive cardiac biopsy for ATTR amyloid, or
 - ii) At least two of the following:
 - (1) Positive extracardiac tissue (e.g., fat-pad, GI tract, etc.) biopsy for ATTR amyloid or positive transthyretin gene mutation associated with amyloid (obtained at any time), or
 - (2) Left ventricle septal wall thickness ≥12 mm by echocardiogram or CMR (in the absence of alternative causes), or
 - (3) Pyrophosphate (PYP) scintigraphy with myocardial uptake ≥grade 2 (or heart/contralateral chest ratio >1.5) using SPECT/CT scan if AL amyloidosis is excluded.

- 4) Able to undergo two PET/CT scans as part of the study, including ability to lie supine for up to 1 hour.
- 5) For women of childbearing potential: agreement to remain abstinent (refrain from heterosexual intercourse) or use contraceptive methods that result in a failure rate of <1% per year during the treatment period and for at least 90 days after the last dose of ¹²⁴I-AT-01.

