9.5 Clinical Laboratory Evaluation

Baseline for clinical chemistry parameters is defined as the most recent laboratory measurement obtained prior to the initiation of study drug. The post-baseline visits are Visit 2 / Week 6 and Safety Follow-up 1 (1-3 days after the second infusion).

Baseline and all post-baseline visit values and change from baseline to post-baseline in laboratory parameters for clinical labs will be summarized for the Safety Set using descriptive statistics, as described in Section 4. Unscheduled visits will be mapped to scheduled visits using analysis windows according to Section 8.1.2.

Biomarkers include NT-proBNP, brain natriuretic peptide (BNP), serum free light chains (only subjects with AL amyloidosis), UACR (only subjects with AL amyloidosis), FLC ratio (Kappa/Lambda) (only subjects with AL amyloidosis), and dFLC (only subjects with AL amyloidosis).

Serum chemistry, Hematology, and biomarker assays will also be presented in data listings for subjects in the Safety Set. The listing will include the reference range (if applicable), classification of high, low, critical, or exclusion, and an abnormal flag. Classification of laboratory values and reference ranges in the data listings will be based on the global laboratory reference ranges used across all sites.

Laboratory parameters with clinically significant changes will be summarized and listed as 'flagged' based on the Sponsor's internal guidelines based on Appendix 14.3.

Additional categorizations of biomarker results for the Image Evaluable Set will be produced including the number and percentage of subjects with:

- Screening and Visit 2 NT-proBNP < 650 ng/L
- Screening or Visit 2 NT-proBNP >= 650 ng/L
- Screening or Visit 2 NT-proBNP >= 650 ng/L and change in NT-proBNP of >= 30% and >= 300 ng/L from Screening to Visit 2
- Screening or Visit 2 NT-proBNP missing
- AL subjects with a normal FLC ratio at Screening and Visit 2

This summary will also include descriptive statistics for dFLC in AL subjects with an abnormal FLC ratio at Screening or Visit 2. NT-proBNP will be displayed in ng/L using the conversion: 1 ng/L = 8.457 pmol/L.Pregnancy test results will also be presented in a data listing for the Safety Set.

Page 24 of 38

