14.3.1.5	Treatment-Emergent Serious Adverse Events by System Organ Class and Preferred Term	Safety
14.3.1.6	Treatment-Emergent Adverse Events Resulting in Study Withdrawal by System Organ Class and Preferred Term	Safety
14.3.1.7	Treatment-Emergent Adverse Events Resulting in Death by System Organ Class and Preferred Term	Safety
14.3.2.1	Summary of Treatment-Emergent Adverse Events on Day of Dosing by Visit	Safety
14.3.2.2	Treatment-Emergent Adverse Events on Day of Dosing by System Organ Class, Preferred Term, and CTCAE Grade by Visit	Safety
14.3.2.3	Summary of TEAEs by Visit	Safety
14.3.2.4	Summary of Hypersensitivity SMQ TEAEs by System Organ Class and Preferred Term by Visit	Safety
14.3.3.1	Laboratory Results: Chemistry	Safety
14.3.3.2	Laboratory Results: Hematology	Safety
14.3.3.3.1	Laboratory Results: Urine and Biomarker Results	Safety
14.3.3.3.2	Laboratory Results: Biomarker Result Categories	Image Evaluable Set
14.3.3.4	Clinically Significant Changes in Laboratory Values	Safety
14.3.4.1	Vital Sign Results	Safety
14.3.4.2	Clinically Significant Changes in Vital Signs	Safety

Page **35** of **38**

Version Date: 2022-12-16 Version: 2.0

Document Control No.: TMP-SA-008-01 Template Effective Date: 23 Mar 2021

Figures		
Number	Title	Population
14.2.1.1	Between Reader Bland Altman Plots of Difference in SUV metrics vs Average of SUV metrics by Visit and Organ	Image Evaluable
14.2.1.2	Between Reader Bland Altman Plots of Difference in SUV metrics vs Average of SUV metrics by Reader, Visit, and Organ and Amyloid Type	Image Evaluable
14.2.1.3	Between Visit Bland Altman Plots of Difference in SUV metrics vs Average of SUV metrics by Reader and Organ	Image Evaluable
14.2.1.4	Between Visit Bland Altman Plots of Difference in SUV metrics vs Average of SUV metrics by Reader and Organ and Amyloid Type	Image Evaluable
14.2.2	Signal to Noise Ratio vs SUV metrics by Reader, Visit, and Organ	Image Evaluable
14.2.3	Contrast to Noise Ratio vs SUV metrics by Reader, Visit, and Organ	Image Evaluable

Listings		
Number	Title	Population
16.2.1	Subject Disposition	All Subjects
16.2.2	Protocol Deviations	Safety
16.2.3.1	Inclusion/Exclusion Criteria Not Met	All Subjects
16.2.4.1	Demographics and Baseline Characteristics	Safety
16.2.4.2	Baseline Disease Characteristics	Safety
16.2.4.3.1	Medical History	Safety
16.2.4.3.2	Surgical or Procedural History	Safety
16.2.4.4	Prior and Concomitant Medications	Safety
16.2.4.5	Prior and Concomitant Medications - Amyloid	Safety

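### SAP 9.5 states the NT-proBNP unit conversion the wrong way round; if pmol/L results are divided by 8.457 as written, the displayed ng/L values are about 71.5 times too low

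*SAP*

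**What the plan says.** SAP 9.5 (Clinical Laboratory Evaluation) gives a single rule for NT-proBNP units: "NT-proBNP will be displayed in ng/L using the conversion: 1 ng/L = 8.457 pmol/L".

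The same section counts subjects in the Image Evaluable Set by NT-proBNP category. One category is below 650 ng/L at both Screening and Visit 2. Another is 650 ng/L or more at either visit. A third is "Screening or Visit 2 NT-proBNP >= 650 ng/L and change in NT-proBNP of >= 30% and >= 300 ng/L from Screening to Visit 2". A fourth is a missing value at either visit. SAP 15.1 lists the output as table 14.3.3.3.2, "Laboratory Results: Biomarker Result Categories".

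Protocol 5.1 uses the same 650 limit in pg/mL, numerically identical to ng/L, as one of five alternative ways to show organ involvement in AL amyloidosis. Neither document states the unit in which the laboratory reports NT-proBNP, and neither gives any other version of the conversion.

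**The concern.** A conversion between mass and molar concentration fixes the molar mass of the analyte. The molar mass implied by this line is that of about one amino acid, whereas the protocol's abbreviation list defines the analyte as "N-terminal prohormone of brain natriuretic peptide". The two units appear to have been swapped.

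The line is operative: it tells the programmer how to obtain the ng/L values that are then compared with 650 and 300 ng/L. If pmol/L results are divided by 8.457 when they should be multiplied, every displayed value shrinks by the same large factor. The error runs one way, because raised values and real absolute changes drop below the limits. The Image Evaluable Set is the set used for repeatability, so a reader may use this table to judge whether cardiac status was stable between the two scans, and would see more stability than there was.

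**Working it through.** **Inputs**

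- Conversion as written: 1 ng/L = 8.457 pmol/L (SAP 9.5).
- Category limits: 650 ng/L, and a change of at least 30% and at least 300 ng/L (SAP 9.5).
- Mass per residue: Protocol 2.2.2 describes AT-01 as a "45 amino acid peptide (MW = 4763.46 Da"), so 4763.46/45 = 105.9 Da per residue.
- Assumptions not in the documents: results arrive in pmol/L, and the program divides by 8.457.

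**Step 1: molar mass implied by the line.** With M in g/mol, pmol/L = ng/L × 1000/M, so M = 1000 × (ng/L)/(pmol/L).

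| Direction | Implied M (g/mol) | Residues at 105.9 Da each |
|---|---|---|
| As written, 1 ng/L = 8.457 pmol/L | 1000/8.457 = 118.2 | 118.2/105.9 = 1.1 |
| Reversed, 1 pmol/L = 8.457 ng/L | 8.457 × 1000 = 8,457 | 8,457/105.9 = 79.9 |

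Only the second row can describe a prohormone fragment. This check needs no outside molar mass. It proves that the direction is wrong. It does not prove that 8.457 is exactly right in the reverse direction.

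**Step 2: size of the error if applied literally.** Take the reversed constant as correct. The right display is pmol/L × 8.457 and the literal display is pmol/L ÷ 8.457. The ratio is 8.457² = 71.52.

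- A true 650 ng/L is 650/8.457 = 76.9 pmol/L and displays as 76.9/8.457 = 9.1 ng/L.
- A true change of 300 ng/L displays as 300/71.52 = 4.2 ng/L.
- To display as 650 ng/L, the true value must be 650 × 71.52 = 46,489 ng/L.
- To display as a 300 ng/L change, the true change must be 300 × 71.52 = 21,456 ng/L.
- Illustration: an AL subject with a true 5,000 pg/mL at both visits displays as 5,000/71.52 = 70 ng/L and is counted as below 650 ng/L at both.

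**Step 3: what does not change.** The 30% limit taken alone is scale-free. A rise from 1,000 to 1,400 ng/L is +40% before and after scaling. The 400 ng/L change, however, displays as 400/71.52 = 5.6 ng/L, so the joint criterion of 30% and 300 ng/L fails.

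**Step 4: sensitivity to the constant.** For a true molar mass M, the error factor is 8.457 × M/1000. Over an assumed range of 7,000 to 10,000 g/mol:

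| Assumed M (g/mol) | Error factor | Display of a true 650 ng/L |
|---|---|---|
| 7,000 | 59.2 | 11.0 |
| 8,457 | 71.5 | 9.1 |
| 10,000 | 84.6 | 7.7 |

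The conclusion is the same across the range.

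**The case against.** The strongest reply is that the harm is hypothetical. If the laboratory reports ng/L or pg/mL, the conversion is never used. If the programmer knows the usual direction and multiplies, the output is right and only the text is wrong. Both points stand, and the 71.5-fold factor has to be stated as conditional. On the other side, a conversion to ng/L has no purpose unless some results come in pmol/L. SAP Appendix 14.3 also works in molar units for glucose and bilirubin. That makes the condition plausible without proving it.

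No study objective depends on the line. The primary endpoint uses SUV data only, and the secondary laboratory endpoint is described in terms of hematology and serum chemistry. Relating images to biomarkers is optional and exploratory, and eligibility is set separately in pg/mL. This stands too: what is at risk is descriptive output.

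The clash with the entry criterion is narrower than it first looks. The 650 pg/mL limit is one of five alternatives for AL subjects and is not an ATTR criterion, and Protocol 5.1 does not require the qualifying value to be the Screening central-laboratory result.

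Finally, SAP 9.5 plans biomarker listings with reference ranges and high/low flags, so a value flagged high but displayed some 70 times too low might be noticed. That lowers the chance of a silent error. It does not correct the instruction.

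**Conclusion.** The conversion is wrong as written. The direction error is certain and follows from the documents alone. No other section corrects it.

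The numerical effect rests on two unstated facts, pmol/L input and literal division, and on 8.457 being the correct reverse constant. Under those assumptions, displayed values are 71.5 times too low (59 to 85 times over the assumed molar-mass range), and the three NT-proBNP categories that use the 650 or 300 ng/L limits become unreliable. The missing-data category, the FLC categories and the repeatability estimates of SAP 8.2 are untouched. The share of subjects affected cannot be given, because the documents contain no NT-proBNP distribution.

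This is a descriptive-output error that should be corrected. It does not threaten the primary analysis.

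**What to change.** 1. Ask the central laboratory for the unit in which it reports NT-proBNP and for its conversion factor. State both in SAP 9.5.
2. If the laboratory confirms the constant, replace the line with: 1 pmol/L = 8.457 ng/L (1 ng/L = 1/8.457 = 0.118 pmol/L). If it reports ng/L or pg/mL, delete the conversion.
3. State which outputs the conversion covers. Besides table 14.3.3.3.2, NT-proBNP appears in the baseline characteristics (SAP 6.2) and in the biomarker tables and listings.
4. Check the constant and its direction in the program for each of those outputs.
5. As a self-test, any AL subject whose qualifying value of at least 650 pg/mL is the Screening result itself, with both visits present, must fall in the category of 650 ng/L or more. This cannot test ATTR subjects or AL subjects who qualified by another route, so also convert a few raw laboratory results by hand.

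The cost is one SAP line, one laboratory query and one constant to check in the program.

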9.6 Vital Signs

Baseline and all post-baseline visit values and change from baseline to post-baseline values in systolic blood pressure, diastolic blood pressure, heart rate, weight, and body mass index (BMI) will be summarized for the Safety Set using descriptive statistics, as described in Section 4. Height at baseline will be summarized using descriptive statistics, as described in Section 4, and will be used in the calculation of BMI at post-baseline visits.

Vital sign results by visit will be presented in a data listing for subjects in the Safety Set.

Vital signs with clinically significant changes will be summarized and listed as 'flagged' based on the Sponsor's internal guidelines based on Appendix 14.3.

